6.1.1 Gynecological Examination

Patients will have gynecological examinations by the Investigator or an authorized designee on Day(s) 0 and 7; or Day(s) 0, 7, and 14 if receiving prolonged treatment, in order to assess presence of BV according to Amsel's criteria. At Day 0, a vaginal sample for bacterial culture will be taken to confirm diagnosis. Symptoms of BV (fishy smell, burning, and irritation) will also be assessed according to a scoring scale (0-3), where 0 = none (absent), 1 = mild (slight), 2 = moderate (definitely present), and 3 = severe (marked, intense). For handling of missing item data in the calculation of the sum of the 3 BV symptoms scores, see [Section 7.1.5](#), and [Section 8.7](#) below.

NOTE: Symptoms of BV (fishy smell, burning, and irritation) will always be assessed by patients themselves, asked by the Investigator at site visits and by the Clinical Trial Unit at telephone visits.

6.1.2 Patient Questionnaire

The questionnaire can be found in [Error! Reference source not found.](#) in the CIP.

The Clinical Trial Unit will call the patients on Day(s) 4, 14 and 35; or Day(s) 4, 11, 21, and 42 if receiving prolonged treatment; and ask questions from the patient questionnaire relating to BV symptoms, usability, concomitant medications, and AEs, if any.

Questions from *Section 1* in the patient questionnaire relating to BV symptoms will be asked to patients over telephone on Day(s) 4, 14, and 35; or Day(s) 4, 11, 21, and 42 if receiving prolonged treatment. A recurrence question will be asked to patients at Days(s) 14 and 35 if not receiving prolonged treatment and at Days(s) 21 and 42 if receiving prolonged treatment.

Questions from *Section 2* in the patient questionnaire relating to usability will be asked to patients on Day 7, and Day 14 if receiving prolonged treatment.

Questions from *Section 3* and *Section 4* in the patient questionnaire relating to concomitant medications and AEs, respectively, will be asked to patients at each visit/telephone contact.

6.2 Safety and tolerability assessments

The below will constitute the local tolerability and safety assessments:

- Adverse events and Serious adverse events (SAEs), and
- Rate of withdrawals from the study and/or the study treatment.

7 Method of analysis

7.1 General

All statistical analyses will be performed in accordance with the ICH E9 guideline for Statistical Principles for Clinical Trials (1), using SAS® (Version 9.4 or higher, SAS Institute Inc., Cary, NC, USA).

7.1.1 Presentation of results

If applicable, results will be presented together with the unit.

Continuous data will be summarised using descriptive statistics, and the following parameters will be reported:

- number of patients with evaluable observations and missing observations
- arithmetic mean and standard deviation
- median
- first and third quartiles
- minimum and maximum.

Categorical data will be presented using absolute frequency and percentage. When the absolute frequency is zero, the percentage will not be presented. Unless stated otherwise, the denominator for percentage calculations will be the total number of patients in the applicable analysis set, including patients with missing data. For variables with missing values, the number and percentage of patients with missing values will be presented.

Statistical testing will be performed using an overall significance level of 5%. The primary endpoint analysis will be based on one-sided testing, whereas the secondary endpoints analyses will be based on two-sided testing. Corresponding confidence intervals will be presented. See Section 7.9 below for further information.

Data will be presented using an appropriate number of decimal places, to ensure that undue precision is not implied (e.g. the number of decimals should not exceed the accuracy of the measuring instrument). Raw data will be presented with the same number of decimals as collected, and derived data with an appropriate number of decimals based on general practice, mathematical rationale or scientific rationale.

Minimum and maximum values will be presented with the same number of decimals as the analysed variable and the other descriptive statistics will be presented with one decimal more. Percentages and proportions will be presented with one decimal. Confidence interval bounds will be presented with the same number of decimals as the corresponding point estimate, and p-values will be presented with 4 decimals or as '<.0001'.

Mock tables and graphs are presented in the Data Display Plan (DDP), which is a supplementary document to this analysis plan. Individual patient data listings will be presented according to the ICH E3 guideline for Structure and Content of Clinical Study Reports (2), unless stated otherwise.

7.1.2 *Baseline*

Unless stated otherwise, the baseline value for a parameter is defined as the last non-missing value before the first self-administration of the study treatment by the patient. The first self-administration is to be performed on the same day as the first study visit (Day 0), after the study visit.

7.1.3 *Analysis relative day*

The analysis relative day for an assessment/value is defined as the time in days from the date of first administration of treatment to the date of the assessment. The date of first administration of treatment is considered as day 0.

7.1.4 *Analysis visit*

An analysis visit is defined as a categorical variable used to classify values within an analysis variable into temporal or conceptual groups used for analyses.

The visits as defined in the case report form, CRF, will be used as analysis visits.

In general, data from unscheduled visits will be presented in data listings only and not included in analysis or summary tables. An exception to this is data used to confirm eligibility in association with screening or randomisation where the last assessment will be considered in summaries of screening data.

7.1.5 *Handling of missing data*

The statistical analysis will be based on the observed data, i.e. no imputation is planned. In case of one or more missing symptom value(s) in the 3 BV symptoms, the sum of the 3 BV symptoms scores will be set to missing, see also [Section 8.7](#) below.

7.1.6 *Interim analyses*

Not applicable.

7.1.7 *Multiplicity*

Although there are two co-primary endpoints, no adjustment of e.g. p-values or confidence intervals will be applied. This is for two reasons, the first being that the evaluation of the second co-primary endpoint (safety and tolerability) will only be based on descriptive statistics and data listings, and the second is that both co-primary endpoints have to show favorable results.

For all other statistical analyses of the secondary endpoints, no adjustment due to multiple testing will be performed. It should be noted that the probability of making a type I error increases with the number of statistical tests performed.

7.1.8 *Subgroups*

Descriptive results of the primary clinical performance endpoint will be presented by study center, and by whether the patients at Day 0 reported 3 or more Bacterial Vaginosis infections during the last 12 months or not.

7.2 *Analysis sets*

The decision on the classification of patients to each analysis set will be taken at the clean file meeting and documented in the clean file report together with the reasons for excluding patients from analysis sets.

7.2.1 *Full analysis set*

Full Analysis Set (FAS): This is the primary population and comprises all patients entering the study and having received at least 1 dose of study treatment. Analyses of clinical performance will be performed against this population.

In addition to this, two sub-populations based on this FAS will be formed: “FAS (For patients not receiving prolonged treatment)”, and “FAS (For patients receiving prolonged treatment)”.

7.2.2 *Per-protocol analysis set*

Per Protocol (PP) Population - This will include all FAS patients without any major protocol deviation, i.e. patients who have completed the study and sufficiently complied with the study protocol, have available primary endpoint data and have received the study treatment according to protocol. The final definition of a major protocol deviation will be decided and defined at the clean file meeting and

documented in the clean file report. If a relevant number of patients are excluded from the PP population, then the analysis of the clinical performance endpoint will be provided for the PP population.

7.2.3 *Safety analysis set*

The safety analysis set will be based on the same definition as used for FAS. All safety analyses will therefore be performed against the FAS. All patients included in the FAS will be accounted for, including those who did not complete the study along with the reasons for withdrawal.

7.3 *Disposition of patients*

The following will be presented:

- Number of screened patients, in total.
- Number of screening failures, in total.
- Number of enrolled patients.

Based on the number of enrolled patients, the following will also be presented:

- Number and percentage of patients who did not receive any dose of study treatment.
- Number and percentage of patients who received at least one dose of study treatment.
- Number and percentage of patients who completed the study.
- Number and percentage of patients who withdrew prematurely from the study.
- Number and percentage of patients in each of the analysis sets.

In addition, a frequency table on the primary reason for premature withdrawal from the study will be presented. Percentages for this table will be based on the number of prematurely withdrawn patients.

The number of patients attending each study visit will also be summarised.

7.4 *Protocol deviations*

Protocol deviations will be presented in a data listing.

The number and percentage of enrolled patients with at least one major protocol deviation leading to exclusion from an analysis set will be presented.

7.5 *Demographics and baseline characteristics*

Summary statistics and frequencies on demographic data (age) and baseline characteristics (pregnancy test, and diagnosis information) will be presented for all analysis sets.

7.6 **Medical history and concurrent diseases**

Medical history and concurrent diseases will be coded according to the Medical Dictionary for Regulatory Activities (MedDRA, version 21.1).

For each system organ class and preferred term, the number and percentage of patients with at least one condition in that system organ class or preferred term will be presented. Medical history and concurrent diseases will be presented in separate tables, based on the full analysis set.

Medical history is defined as events stopped prior to baseline. Concurrent diseases are defined as ongoing events and events stopped on or after baseline. If the start and/or stop date is partially unknown, the following imputation rules will be used for the purpose of classifying the events:

	Imputed start date	Imputed end date
Unknown year	Missing	Missing
Unknown month	1 January	31 December
Unknown day	First of month	Last of month

If it is not possible to classify the condition based on the reported and/or imputed start and end dates, it will be considered as concurrent. In data listings, the dates will be presented as reported.

7.7 **Prior and concomitant medication**

Medications will be coded according to the World Health Organisation (WHO) Drug Dictionary and summarised by therapeutic subgroup (ATC level 2) and preferred name.

For each therapeutic subgroup and preferred name, the number and percentage of patients who used at least one medication of that therapeutic subgroup or preferred name will be presented. Prior and concomitant medications will be summarised in separate tables, based on the full analysis set.

If a reported medication cannot be coded with a preferred name, the lowest available higher-level dictionary term will be used instead in the summary tables. If a medication cannot be coded on a lower level than the therapeutic subgroup or the anatomical main group (ATC level 1), that medication will be presented as 'Not codable' under that therapeutic subgroup/anatomical main group.

Prior medication is defined as medication stopped prior to baseline. Concomitant medication is defined as ongoing medication or medication stopped on or after baseline. If the start and/or stop date is partially unknown, the following imputation rules will be used for the purpose of classifying the medication:

	Imputed start date	Imputed end date
Unknown year	Missing	Missing
Unknown month	1 January	31 December
Unknown day	First of month	Last of month

If it is not possible to classify a medication based on the reported and/or imputed start and end dates, it will be considered as concomitant. In data listings, the dates will be presented as reported.

Any use of rescue medication will be identified as any concomitant medication used with “Indication (reason for medication)” equal to “Rescue medication” as recorded in the CRF.

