Below follows a list of all secondary endpoints followed by information on which are binary and which are continuous. Note that, as described in [Section 3.2.1](#) above, the analyses of the secondary endpoints will be performed on 3 different patient categories. These are denoted as A, B, and C below.

A. All patients

- i] Proportion of patients being negative for each of the 3 Amsel criterion on Day 7 compared to Day 0
- ii] Proportion of patients having a reduction in the sum of the 3 BV symptoms scores (fishy smell, burning, and irritation) on Day 4 and Day 7, compared to Day 0
- iii] Change in the sum of the 3 BV symptoms scores (fishy smell, burning, and irritation) from Day 0 to Day 4 and Day 7
- iv] Proportion of patients receiving prolonged treatment
- v] Usability, measured by patient questionnaire

The endpoints i], ii], iv], and the first 4 questions in endpoint v] are binary variables.

The endpoints iii], and the 5th question in v] are considered as continuous variables.

B. For patients not receiving prolonged treatment

- vi] Recurrence rate on Day 14 and Day 35, defined as the proportion of patients clinically cured on Day 7 and thereafter responding "yes" to a yes/no question from the patient questionnaire on whether the symptoms have recurred

The endpoint vi] constitute binary variables.

C. For patients receiving prolonged treatment

- vii] Clinical cure rate on Day 14, defined as the absence of all of the 3 Amsel criteria as defined above
- viii] Proportion of patients being negative for each of the 3 Amsel criterion on Day 14 compared to Day 0
- ix] Proportion of patients having a reduction in the sum of the 3 BV symptoms scores (fishy smell, burning, and irritation) on Day 11, Day 14, Day 21, and Day 42, compared to Day 0
- x] Change in the sum of the 3 BV symptoms scores (fishy smell, burning, and irritation) from Day 0 to Day 11, Day 14, Day 21, and Day 42
- xi] Recurrence rate on Day 21, and Day 42, defined as the proportion of patients clinically cured on Day 14 and thereafter responding “yes” to a yes/no question from the patient questionnaire on whether the symptoms have recurred
- xii] Proportion of patients receiving rescue treatment on Day 14

The endpoints vii], viii], ix], xi], and xii] are binary variables.

The endpoints x] are considered as continuous variables.

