8.8 Recurrence rate

Recurrence rate is based on a binary variable, where a recurred patient is defined as a patient clinically cured on Day 7 and thereafter responding "yes" at specified follow-up visits to a yes/no question from the patient questionnaire on whether the symptoms have recurred.

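### SAP 8.8 ties recurrence to Day 7 cure only and names no denominator, so the Day 21/42 rate is zero by definition or, with the Day 14 anchor and the default denominator, diluted by women never cured

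*SAP*

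**What the plan says.** Four parts of the SAP together determine the recurrence rate.

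- **Default denominator (7.1.1, Presentation of results).** Unless another basis is given, "the denominator for percentage calculations will be the total number of patients in the applicable analysis set, including patients with missing data".
- **Analysis sets (7.2.1, Full analysis set).** From the FAS, "two sub-populations based on this FAS will be formed": women who do and women who do not receive prolonged treatment. No set of clinically cured women is defined.
- **Endpoints (7.9.2).** The SAP notes that "the analyses of the secondary endpoints will be performed on 3 different patient categories": A (all), B (no prolonged treatment) and C (prolonged treatment). Endpoint vi (category B, Day 14 and Day 35) is "defined as the proportion of patients clinically cured on Day 7 and thereafter responding" yes to the recurrence question. Endpoint xi (category C) reads: "Recurrence rate on Day 21, and Day 42, defined as the proportion of patients clinically cured on Day 14 and thereafter responding" yes.
- **Derivation (8.8).** "Recurrence rate is based on a binary variable, where a recurred patient is defined as a patient clinically cured on Day 7", who then answers yes at a specified follow-up contact. Day 14 cure is not mentioned, and neither is a denominator.

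SAP 4 (Study design) adds that prolonged treatment goes to women not cured at Day 7, and that those still not cured at Day 14 receive an antibiotic. The protocol (2.2, 6.1) words the endpoints in the same way and names no denominator either.

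**The concern.** A recurrence rate only makes sense among women who were cured. Under the SAP's rules, cure enters the definition of the event (8.8), while the denominator is left to a default that takes in the whole set (7.1.1). In the prolonged-treatment group the plan itself expects some women to remain uncured on Day 14. Each of them lowers the reported rate, so a less effective second course would appear to have less recurrence.

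The derivation in 8.8 also fits only endpoint vi. Applied as written to endpoint xi, it requires cure on Day 7 in a group selected for not being cured on Day 7. Two programmers following the SAP could therefore report different Day 21/42 rates, each with a defensible reference to the text.

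**Working it through.** **Inputs.** Planned N is 24 and the assumed Day 7 cure rate is 70 % (SAP 5.1). The interval is a two-sided 95 % Clopper-Pearson interval (SAP 7.9.2). The plan gives no recurrence figure to reproduce, and it states neither a Day 14 cure rate nor a recurrence rate. Those counts are assumptions below and are varied.

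**Size of the groups.** Expected to receive prolonged treatment: 24 × 0.30 = 7.2, taken as 7. Expected cured on Day 7: 24 × 0.70 = 16.8, taken as 17.

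**Step 1: 8.8 read literally at Day 21/42.** Members of the set were not cured on Day 7. A recurred patient must have been cured on Day 7. Unless there is a protocol deviation, no woman meets both conditions, so the count is 0 of 7 whatever the women answer. Endpoint xi, with its Day 14 anchor, can give a count above zero from the same data.

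**Step 2: Day 14 anchor with the 7.1.1 default.** Let m be the number in the set, c the number cured on Day 14, and x the number cured who later answer yes. Then

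reported rate = x/m = (x/c) × (c/m).

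The cured-only rate x/c is multiplied by the share cured, c/m. For m = 7:

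| Cured c | Recurring x | Default x/7 (95 % CI) | Cured-only x/c (95 % CI) | Factor c/7 |
|---|---|---|---|---|
| 2 | 1 | 14.3 % (0.4 to 57.9) | 50.0 % (1.3 to 98.7) | 29 % |
| 3 | 1 | 14.3 % (0.4 to 57.9) | 33.3 % (0.8 to 90.6) | 43 % |
| 4 | 2 | 28.6 % (3.7 to 71.0) | 50.0 % (6.8 to 93.2) | 57 % |
| 6 | 1 | 14.3 % (0.4 to 57.9) | 16.7 % (0.4 to 64.1) | 86 % |
| 7 | 1 | 14.3 % (0.4 to 57.9) | 14.3 % (0.4 to 57.9) | 100 % |

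One recurrence is reported as 14.3 % whether it is one of two cured women or one of seven. The size of the set also matters: with 4 cured and 2 recurring, the default gives 2/5 = 40.0 % in a set of 5 and 2/9 = 22.2 % in a set of 9, while the cured-only rate stays at 50.0 %.

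**Step 3: which n goes into the interval.** SAP 7.1.1 includes women with missing data. SAP 7.1.5 bases the analysis on observed data. Suppose 7 women, 4 cured, 2 recurring, and 1 cured woman not reached. The candidate denominators are then:

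- 7 (whole set): 28.6 %
- 6 (whole set, observed): 2/6 = 33.3 %
- 4 (cured): 50.0 %
- 3 (cured and observed): 2/3 = 66.7 %

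The observed-data rule alone does not remove uncured women, because protocol 3.5.11 and 3.5.13 put the recurrence question to everyone on prolonged treatment.

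**Step 4: Day 14/35.** This group is by design cured on Day 7. SAP 8.9 counts prolonged treatment by whether a dose was taken on Day 7, 9, 11 or 13. A woman uncured or unassessed on Day 7 who took none of these doses would therefore fall into this group. With 17 cured and, by assumption, 5 recurring, the cured-only rate is 5/17 = 29.4 % (10.3 to 56.0). One, two or three such extra women give 5/18 = 27.8 %, 5/19 = 26.3 % and 5/20 = 25.0 %. The factor is at worst 17/20 = 85 %.

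**The case against.** The best answer is that the endpoint is already conditional. The wording "defined as the proportion of patients clinically cured on Day 14 and thereafter responding" yes can be read as a proportion among cured women. Since 7.1.1 yields wherever something else is stated, that wording might count as the exception. The default also sits in a section on presenting results, 7.9.2 does not give the n for the interval, and the mock tables are in a Data Display Plan that is not among the documents.

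This has force, and it rules out several stronger inferences a reader might draw:

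- **That the SAP unambiguously keeps never-cured women in the rate.** The stated rules lead there, but the conditional reading is open. SAP 8.8 also does not say whether an uncured woman is coded no or not applicable.
- **That women not reached count as not recurred.** SAP 7.1.1 has them shown as missing, and 7.1.5 rules out imputation. They may enlarge a denominator, but they are not recoded.
- **That the interval is certainly computed on the wrong n.** The n is unsettled, which is a different fault.
- **That Day 14/35 is seriously biased.** SAP 4 describes that group as the women cured at Day 7, so few others can enter it.
- **That a planned comparison with the antibiotic figures in protocol Table 1 is spoiled.** No such comparison is planned.

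The stakes are also limited. No hypothesis test is made on binary secondary endpoints, and Day 14 cure is reported separately as endpoint vii. In a group of about 7, a careful reader could recover the conditional rate from the tables and listings.

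Two things remain. The SAP does state a different basis when it wants one: 7.3 bases percentages for withdrawal reasons on the withdrawn patients, and 8.6 expressly sets Day 0 status aside. For recurrence it states none. And the conflict between Day 7 in 8.8 and Day 14 in endpoint xi does not depend on how the denominator is read.

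**Conclusion.** The point holds for the Day 21/42 recurrence rate. SAP 8.8 contradicts endpoint xi and, taken literally, makes that rate zero by definition. With the Day 14 anchor, the rules as stated multiply the cured-only rate by the share of the prolonged-treatment group cured on Day 14: 29 % to 86 % of its value if 2 to 6 of 7 women are cured. There is no dilution if all are cured, and none to see if nobody recurs. The group size of 7 follows from the plan's own 70 % assumption; the cured and recurring counts are illustrative. Because the endpoint wording and 7.1.5 pull away from the default, the denominator for the rate and its interval must be treated as unsettled. The effect on Day 14/35 is small. This concerns a secondary, descriptive endpoint and should be corrected, but it does not touch the primary analysis.

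**What to change.** Replace the definition in SAP 8.8 with text such as:

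> A recurred patient is one clinically cured at the qualifying visit (Day 7 for endpoint vi, Day 14 for endpoint xi) who answers yes at the specified contact. Overriding 7.1.1, the denominator for the rate and its Clopper-Pearson interval is the patients clinically cured at that visit who answered the question; cured patients with no answer are reported separately.

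A sensitivity analysis that counts cured women with no answer as recurred is optional.

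The cost is a change of SAP wording and of the denominator in the recurrence tables; no new data are needed. The downside for the sponsor is a higher recurrence rate with a wider interval, on few women.

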5.1 Sample size

Assuming the true cure rate is equal to 70 %, 22 patients are needed to obtain 90 % chance (90 % power) to show that the one-sided 95 % CI for the observed cure rate is above 40 %. To compensate for a small number of non-evaluable patients, 24 patients will be included.

6 Assessments

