7.9 Primary and secondary endpoints analyses

All analyses of clinical performance endpoints will be performed on the full analysis set, and these analyses will be considered as the main analyses. If a relevant number of patients are excluded from the PP population, the per-protocol analysis set will be used for supportive clinical performance sensitivity analysis of the primary clinical performance endpoint.

If the stated assumptions that the statistical evaluation is built upon can be questioned, suitable alternative methods may be applied. For example, a 95% confidence interval based on a non-parametric method may be applied if assumption of data belonging to the normal distribution seems not to hold.

All study endpoints (primary, secondary, and exploratory), as well as the related variables specified in the list below in Section 7.9.2, will be presented descriptively.

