7.9.1 Primary endpoints

- Clinical performance endpoint: Clinical cure rate on Day 7 will be calculated and presented together with a one-sided 95 % confidence interval based on the exact binomial distribution (Clopper-Pearson).
- Clinical safety endpoint: Safety and tolerability will be assessed according to Section 7.10.2.

The primary clinical performance endpoint is the Clinical cure rate on Day 7, where clinical cure is defined as the absence of all of the Amsel criteria stated in [Section 3.1.1](#) above. The primary performance objective of the trial is to show that the Clinical cure rate is above 40 %, *i.e.* to show that the lower limit of the one-sided 95 % CI for the observed cure rate is above 40 %.

Hypotheses for the primary clinical performance endpoint

Null hypothesis: Clinical cure rate is less than or equal to 40 %.

Alternative hypothesis (one-sided): Clinical cure rate is above 40 %.

The primary clinical safety endpoint, i.e. safety and tolerability based on reported treatment-emergent AEs, will be analysed descriptively only, see Section 7.10.2 below, and will thus not be connected to any formal hypothesis testing.

7.9.2 *Secondary clinical performance endpoints*

The secondary clinical performance endpoints are either binary or continuous.

The usability data, as measured by the patient questionnaire and which contain both binary and continuous endpoints, will only be presented descriptively.

The other binary secondary clinical performance endpoints will be calculated and presented together with a two-sided 95 % confidence interval based on the exact binomial distribution (Clopper-Pearson). No hypothesis testing will be made on the binary endpoints.

The only remaining clinical performance endpoint that is considered as a continuous endpoint is the change in the sum of the 3 BV symptoms scores. Here, applying Student's t distribution, a two-sided 95% confidence intervals for the arithmetic mean will be presented.

Hypothesis for the continuous secondary clinical performance endpoint "Change in the sum of the 3 BV symptoms scores"

Null hypothesis: Change from baseline is = 0.

Alternative hypothesis (two-sided): Change from baseline \neq 0.

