8.5 Clinical cure rate

Clinical cure rate is based on a binary variable, where a clinically cured patient is defined as absence of all of the following Amsel criteria:

- Thin, white, yellow, homogenous discharge
- Clue cells on microscopy (more than 20% of epithelial cells)
- Release of fishy odor "i.e. a positive whiff test" when alkali (10% potassium hydroxide [KOH] solution) is added

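### SAP 7.1.1 and 7.1.5 imply different n for the Day 7 Clopper-Pearson limit when a dosed patient is not assessed, and the 90 % power in 5.1 is not what the exact limit gives

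*SAP*

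**What the plan says.** **Passages that point to all dosed patients.** SAP 7.1.1 sets a default, which applies unless something else is stated: "the denominator for percentage calculations will be the total number of patients in the applicable analysis set, including patients with missing data". SAP 7.9 adds that "All analyses of clinical performance endpoints will be performed on the full analysis set". SAP 7.2.1 defines that set as everyone who entered and took at least one dose. A Day 7 assessment is not required; only the per-protocol set in 7.2.2 asks that patients "have available primary endpoint data and have received the study treatment according to protocol".

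**Passages that point to assessed patients.** SAP 7.1.5 says: "The statistical analysis will be based on the observed data, i.e. no imputation is planned". SAP 5.1 derives a need for 22 patients and then says: "To compensate for a small number of non-evaluable patients, 24 patients will be included".

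**Passages that should decide.** SAP 7.9.1 says "Clinical cure rate on Day 7 will be calculated and presented together with a one-sided 95 % confidence interval", names Clopper-Pearson, and makes a lower limit above 40 % the performance objective. SAP 8.5 says "Clinical cure rate is based on a binary variable, where a clinically cured patient is defined as absence of all" of the three listed Amsel criteria. Neither gives the n or says how an absent Day 7 assessment is classed.

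**Protocol.** Section 9 begins from observed data. It then allows for measures that reduce bias, or direct it conservatively, if missing data are judged to be an issue. It therefore supports both readings, and it leaves the detail to the SAP.

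**The concern.** The Day 7 cure rate carries the only formal success criterion, in an open-label single-arm study. If two denominators can both be defended from the SAP, the choice between them could be made with the cure count already known.

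A missing Day 7 assessment is foreseeable. Protocol 3.6 provides for telephone contact with patients who refuse a site visit, and a call yields no Amsel examination. Protocol 4.7 rules out replacement. The SAP gives an explicit rule for missing symptom items, which feed secondary endpoints (7.1.5 and 8.7), but none for the primary endpoint.

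The 22-plus-2 reasoning in 5.1 also depends on which n is analysed. Checking it shows that the stated power does not belong to the planned exact limit.

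**Working it through.** **Inputs.** Threshold 40 %, one-sided 95 % Clopper-Pearson limit (SAP 7.9.1); assumed true rate 70 %, 22 needed, 24 included, 90 % power (SAP 5.1, Protocol 9.3).

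**1. The plan's own figure.** The normal approximation gives n = [(1.645·√(0.4·0.6) + 1.282·√(0.7·0.3)) / (0.7 − 0.4)]² = 21.56, rounded up to 22. The stated 22 is reproduced, but by a method other than the planned analysis.

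**2. Power under the planned limit.** The lower limit for x cures in n is the 5th percentile of Beta(x, n − x + 1). It exceeds 40 % exactly when P(X ≥ x | n, 0.40) < 0.05.

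| n | Cures needed | Error at 40 % | Power at 70 % |
|---|---|---|---|
| 22 | 14 | 2.1 % | 81.4 % |
| 23 | 14 | 3.5 % | 88.0 % |
| 24 | 15 | 2.2 % | 84.7 % |

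None of these reaches 90 %.

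**3. Which counts depend on n, with 24 dosed.**

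| Cures | n = 24 | n = 23 (1 missing) | n = 22 (2 missing) |
|---|---|---|---|
| 13 | 35.8 %, fails | 37.5 %, fails | 39.5 %, fails |
| 14 | 39.7 %, fails | 41.7 %, succeeds | 43.9 %, succeeds |
| 15 | 43.7 %, succeeds | 46.0 %, succeeds | 48.5 %, succeeds |

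Only 14 changes verdict. With three or four missing, the cut-off among assessed patients falls to 13 (n = 21 or 20), so 13 and 14 are both affected.

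**4. With 23 dosed.** The full-set cut-off is 14. One missing gives n = 22, also with cut-off 14, so no count is affected. Two missing gives n = 21 with cut-off 13, so the affected count is 13 (13/23 limit 37.5 %, 13/21 limit 41.7 %).

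**5. Chance of a disputed result and power of each rule.** Take 24 dosed, a true rate of 70 %, and missingness unrelated to outcome (an assumption).

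| Missing | P(exactly 14 cures) | Power, full set (needs 15) | Power, assessed only (needs 14) |
|---|---|---|---|
| 1 | 10.9 % | 77.1 % | 88.0 % |
| 2 | 14.2 % | 67.1 % | 81.4 % |

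**6. Type I error.** No dropout rate is documented, so these are assumed ranges. Each case enumerates 24 dosed patients at a true rate of 40 %.

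| Who misses Day 7 | Assumed rate in that group | Error, assessed only | Error, full set |
|---|---|---|---|
| Only non-cured | 5 / 10 / 20 % | 3.5 / 4.8 / 8.2 % | 2.2 % throughout |
| Unrelated to outcome | 5 / 10 % | 2.8 / 2.8 % | 1.3 / 0.7 % |
| Only cured | 5 / 10 % | 1.9 / 1.5 % | 1.3 / 0.7 % |

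In the first row the error passes 5 % only at about 11 % missing. The 20 % case implies 24 × 0.6 × 0.2 = 2.9 expected missing, above the plan's allowance of 2.

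**The case against.** The strongest reply is that the SAP already answers the question. The 7.1.1 default covers percentages, the cure rate is a percentage presented with its interval, and the natural reading is one n for both. SAP 7.1.5 names no denominator, and its only worked rule concerns the symptom sum. Under 8.5 a patient who was not examined has not been shown to be cured. Much of this stands: a reader might infer that the SAP has no denominator rule at all, and 7.1.1 shows that it has one. What remains is that 7.1.1 concerns presentation and yields to anything stated otherwise. A programmer could take 7.1.5 as such a statement, because scoring an unobserved patient as not cured is hard to square with planning no imputation.

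A reader might also infer that an observed-case analysis inflates the error rate. The documents do not support that. It exceeds 5 % only if non-cured patients selectively stay away at about 11 % or more, and Protocol 3.5.5 dispenses prolonged treatment at the Day 7 visit, which gives them a reason to attend.

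Two further points limit the harm. SAP 7.1.1 requires that "For variables with missing values, the number and percentage of patients with missing values will be presented", so a reader could recompute the limit. The Data Display Plan, not available here, may show the denominator. Neither fixes in the SAP the n for the decision limit.

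**Conclusion.** The concern holds as an unreconciled conflict: 7.1.1 with 7.9 and 7.2.1 implies all dosed patients, 7.1.5 and 5.1 point to assessed patients, and neither 7.9.1 nor 8.5 chooses. The wording in 5.1 is itself ambiguous, since non-evaluable could include enrolled patients who were never dosed, whom 7.3 counts separately.

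The size is modest. The verdict turns on n only at a borderline count, and 14 is that count only if exactly 24 are dosed and one or two are missing. A reader might infer that 14 cures is always the disputed result; with 23 dosed it is not. The direction of any bias is unknown.

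The power statement is a firmer error and needs no missing-data assumption. With the planned exact limit and a true rate of 70 %, power is 81.4 % at 22 and 84.7 % at 24, against the stated 90 %. This does not show that 24 is too few for a feasibility study, only that the figure is wrong. Both parts should be fixed.

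**What to change.** - **SAP 7.9.1, with matching words in 7.1.5 and 8.5.** Before data are reviewed, state one n for both the cure rate and its Clopper-Pearson limit. Using the full analysis set, with a missing Day 7 assessment counted as not cured, follows the 7.1.1 default. This is a choice the documents support but do not force; either rule, once stated, removes the ambiguity.
- **Sensitivity analysis.** Name the observed-case result and report it beside the primary one.
- **SAP 5.1, Protocol 9.3 and the protocol synopsis.** Replace 90 % power with 81.4 % at n = 22 (14 cures needed) and 84.7 % at n = 24 (15 needed). Say what non-evaluable means under the chosen rule. Do not raise the sample size.

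The cost is a few sentences and one table. The full-set rule has a real downside: if missingness is unrelated to outcome, it biases the reported rate downward and lowers power to 77 % from 88 % with one missing, and to 67 % from 81 % with two. That is the reason to show the observed-case result alongside it.
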